12. ETHICAL CONSIDERATIONS

Prior to conducting the study, this protocol will be submitted to the evaluation of the CREC (Clinical Research Ethics Committee) from OSI Bilbao Basurto. The patients included in the study will not be subjected to any risk other than that which they must suffer from the usual medical care of their disease and that due to the disease itself. No patient will be included or any study procedure will be carried out until the informed consent in writing has been obtained after written and oral information (Annex II: Information to the patient and informed consent).

The information procedure will consist of the following phases:

- a) In the presence of the patient, the Information Sheet and Informed Consent will be read aloud in a clear and concise manner
- b) All doubts that may arise will be clarified
- c) Sufficient time will be allowed for patient to sign the Informed Consent

Participation in the study will not entail any extra expense on the part of the patient. The study will not begin in any center until the Managing Director of the same has given his express authorization to it.

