3.2 Advantages of the 3D orthosis

The development of the 3D bio-splint is a project opportunity for a new 3D orthosis that will allow a qualitative leap in the search for an intelligent solution for patients with rhizarthrosis.

The splints developed using this method have a series of advantages both in manufacturing and for patients, among which we can highlight:

- Increase the precision in the design of the splint to place it in the affected area.
- Reduce the weight of the splint in order to lead a more agile life.
- Improve perspiration.
- Resistance to water, which will improve hygiene, the patient can even bathe with the splint on.
- Greater mobility. The “pincer” movement will not be affected.
- Allow air circulation.
- Improve aesthetic appearance: simple splint design that can be covered if the patient considers it so, for example, with gloves.
- Manufacturing times: the 3D model is made in 3 hours and can be in use by the patient in 72 hours.
- It can be made with fully recyclable materials.

Below is a comparative summary table of the advantages of the 3D orthoses compared to current “conventional” orthoses:

CONVENTIONAL ORTHOSES' ASPECTS TO IMPROVE		ADVANTAGES OF 3D ORTHOSES
Standard orthosis sizes.	Comfort of the affected patient.	-Customized splint adapted to the anatomy of each patient. (Scan to obtain 3D model of affected anatomy and fully customized CAD design).
Thermoplastic Materials / PP / Plastic Cloth (Nylon)	Heavy orthosis. Causes excessive heat and sweating.	-Lightened splint both with the material and its density (possibility to edit the internal density of the material). -The range of materials offered by additive manufacturing will allow testing different materials and considering the most appropriate in terms of their rigidity-flexibility.
PP manufacturing process	Difficulty in manufacturing the PP (see section 3.1.)	-Additional manufacturing is a simple process by which the structure of the orthosis can be manufactured without any problem by melting the plastic and creating the 3D layer by layer. This technique gives total freedom to the design, being able to create pieces unthinkable with other manufacturing methods.
Manufacturing times		Fabrication of an orthosis can be finished in 3 hours approximately.
Usually closed orthosis design	Causes excessive heat and sweating.	-Orthosis design freedom: openings / holes ...

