6. DESIGN OF THE STUDY

This study is a **proof of concept or feasibility study**. As such, the study tries to find out if the personalized splint can be suitable for the treatment of patients with osteoarthritis of the TMJ and obtain at least similar results, providing greater comfort of use and facilitating an improvement in the development of life activities daily to patients. Therefore, it is not a design aimed at evaluating the efficacy of such treatment.

Prospective study with two arms, open with 1: 1 allocation.

The study will be carried out in the outpatient clinics of the OSI Bilbao-Basurto Orthopedic Surgery and Traumatology Service with the collaboration of the Rehabilitation Service.

The study will include a recruitment visit and two follow-up visits, one after the first month and another final visit at the 3-month period

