8. SAMPLE SIZE

This study has not been designed to test specific statistical hypotheses, so there is no justification for the sample size, since the study is designed as a proof of concept. It is intended to include 20 patients in each treatment arm.

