10. FOLLOW-UP AND DATA COLLECTION

The data will be collected in three visits. The baseline visit, in which the inclusion / exclusion criteria are checked and the corresponding treatment is assigned.

In the control branch, the doctors prescribe the usual splint for each patient. In the intervention branch the personalized splint.

At the baseline visit, the patients will be clinically examined, an X-ray will be taken to verify the inclusion criteria, and the DASH, VAS for pain, and pressure force will be completed.

On the second visit, one month after the splint, pain, satisfaction, DASH, wearing time and grip strength will be evaluated.

At the third follow-up visit (end of the study) that will take place at the third month of follow-up (between 11-14 weeks), patients will complete the DASH questionnaire, the VAS pain scale (from 0-no pain to 10-worse imaginable pain), the pressure force, the time of use and the satisfaction questionnaire made up of 6 items, on an 11-point scoring scale, in which satisfaction will be assessed.

The data of the patients and of the study variables will be collected by the specialists of each of the centers involved in the study. These data will be collected in a data collection notebook and entered into a database designed and adapted for this study.

At the end of the data collection, the errors they may contain will be eliminated by checking logical ranges and detecting impossible codes. Likewise, any errors found will be corrected by checking the clinical history. Once it is considered that the data are refined, they will be closed for statistical analysis.

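### No planned variable identifies splint-related harm or device failure, and the statement that patients face no added risk is too absolute for the arm given a new device

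*Protocol*

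**What the plan says.** Protocol Section 12 (Ethical considerations) states that included patients "will not be subjected to any risk other than that which they must suffer from the usual medical care", apart from the risk of the disease itself. The sentence makes no distinction between the arms.

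Section 6 (Design) describes a "Prospective study with two arms, open with 1: 1 allocation", and Section 8 (Sample size) adds that "It is intended to include 20 patients in each treatment arm". Section 3.2 introduces the experimental splint with the words that it "is a project opportunity for a new 3D orthosis". Section 6 gives the purpose: "the study tries to find out if the personalized splint can be suitable for the treatment of patients".

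Section 9 lists what is recorded: pain on the VAS, DASH, a six-item satisfaction scale, daily hours of use by direct question, grip and pinch strength, and demographic variables. Section 10 sets the visits. At one month, "pain, satisfaction, DASH, wearing time and grip strength will be evaluated". At three months the same domains are collected again. Section 11 analyses pain, DASH, time of use and satisfaction, and has no harm summary. Annex IV reproduces the VAS, the DASH with its optional modules, and the satisfaction questions.

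**The concern.** A feasibility study of a worn device should show whether patients can keep wearing it, and if not, why. The plan records how long the splint is worn and how satisfied the patient is. It has no place for the reason behind a short wearing time or a low score. A pressure sore, a cracked splint, a remake and mild dislike would look alike in the data. A patient who gave up the splint because of a problem might leave only low hours of use, poorer scores or a missed visit.

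The Section 12 sentence adds to this. If no extra risk is assumed, there seems to be no reason to look for any. The protocol offers no evidence for that assumption in the arm given the new splint. A common device problem could therefore go uncounted and be carried into a later, larger study.

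**Working it through.** **Is a harm variable planned?** The protocol gives no safety figure to reproduce, and Section 8 says of the sample size: "This study has not been designed to test specific statistical hypotheses, so there is no justification for the sample size". The check is therefore a reading of the sections that define the data.

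- Section 9 (variables): pain, function, satisfaction, hours of use, strength, demographics. No adverse-event, skin, breakage, refitting or discontinuation variable.
- Section 10 (visits): the same outcomes at one and three months, with no question about problems.
- Section 11 (analysis): group comparisons, within-group change and a baseline-adjusted model. No harm counts.
- Sections 7, 13 and 14 and Annex III: eligibility, scanning, limitations and recruitment. No harm procedure.
- Annex V: the appended Declaration of Helsinki mentions serious adverse events in general terms. It is a statement of principles and creates no study procedure or data field.

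**What could show harm indirectly?** The VAS could show worsening pain. DASH items 24 to 28 cover pain, pain on activity, tingling, weakness and stiffness. Satisfaction item 5 asks about comfort. Hours of use could show that a splint was abandoned. None of these records a cause, a date, an outcome or a link to the splint.

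**Who is exposed?** With 20 per arm, 20/40 = 50% of patients wear the new device.

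**What could 20 patients show if problems were recorded?** The true rates p below are assumptions, since the documents give none. All 20 patients are assumed to be asked. The chance of at least one event is 1 − (1 − p)^20:

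| Assumed rate p | Calculation | P(at least one in 20) |
|---|---|---|
| 5% | 1 − 0.95^20 | 64% |
| 10% | 1 − 0.90^20 | 88% |
| 20% | 1 − 0.80^20 | 99% |

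If no event were recorded in 20, the exact two-sided 95% upper limit would be 1 − 0.025^(1/20) = 0.168, or 16.8%.

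So even this small arm could reveal common problems and put a ceiling on their rate. Neither is possible without a field that counts them.

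**The case against.** The case on the other side has real weight, and it limits the point in five ways.

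1. **Some tolerability data are collected.** A reader might infer that the study will have no safety information at all. The documents do not support that: the VAS, the DASH symptom items (tingling included), the comfort item and the hours of use all bear on tolerability. What is missing is identification and attribution.
2. **Section 12 is not shown to be false.** Section 7 requires that a splint already be clinically indicated, both arms wear an external thumb splint, and the scan takes about a minute. The sentence can be read as saying that the risks are of the usual kind, and the protocol names no specific hazard. It is fair to call the wording too absolute and unsupported for the 3D arm, but not to call it a proven error.
3. **No experiment on materials is planned.** Section 3.2 says that the range of printable materials "will allow testing different materials and considering the most appropriate in terms of their rigidity-flexibility". A reader might take this as testing on participants. It stands in a table of the general advantages of additive manufacturing, and no study procedure does this. Likewise, Section 3.3 names the avoidance of health problems as a design aim, which does not concede extra risk.
4. **Annex IV is not the whole notebook.** As shown, it also lacks hours of use and strength, which Sections 9 and 10 require. Absence from it proves little, so the point rests on Sections 9 to 11.
5. **Some pages are not available.** They lie between Sections 1 and 2 and ahead of Annex III, where Section 12 places the patient information as Annex II. They may describe device risks or how to report them, and their content cannot be known.

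These objections do not supply a harm variable in the sections that define variables, visits and analysis. Nor could a separate statistical analysis plan fill the gap, because it cannot summarise data that are not collected.

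**Conclusion.** The point holds in this form: Sections 9 to 11 plan no variable that identifies splint-related harm or device failure, so the suitability of a new device would be judged without harm counts. The Section 12 assurance is too absolute, and unsupported, for the 20 of 40 patients given that device.

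The conclusion rests on the sections available and on reading Sections 9 and 10 as the list of what is collected. The probabilities and the upper limit show what the planned arm could reveal if problems were recorded. They are not estimates of how often the splint causes trouble, and they would weaken if fewer than 20 patients were followed. The change should be made before data collection, but it does not call the pain comparison into question.

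**What to change.** - **Sections 9 and 10 and the notebook:** add one item at the 1- and 3-month visits, in both arms, recording any splint-related problem (for example skin or pressure trouble, breakage, refitting), with its type, date and outcome, and whether wear stopped because of it.
- **Section 11:** report the number of patients with any such problem, by arm, with exact 95% limits, as description only.
- **Section 12:** reword the sentence to say that the 3D splint may carry device-related risks, which will be recorded.

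The cost is one extra notebook item at each of two existing visits, one table and one revised sentence. No visit or examination is added. Asking the same question in both arms matters because the study is open: problems sought only in the 3D arm could not be compared with those of the usual splint.

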13. DESCRIPTION OF THE TECHNIQUE TO BE USED IN THE STUDY

The project will be carried out in the outpatient clinics of the OSI Bilbao-Basurto Orthopedic Surgery and Traumatology Service with the collaboration of the OSI Rehabilitation Service.

This study will include a recruitment visit and two follow-up visits, one at first month and another final visit at 3 months.

Patients with a new diagnosis of osteoarthritis of the trapeziometacarpal joint will be included. One group of patients will wear the usual splint indicated by the staff physicians and the other group, the personalized splint designed by the company OPTIMUS 3D.

The main variable is pain, which will be measured, as is usual practice, by a visual analog scale (VAS). In addition, the DASH (Disabilities of the Arm, Shoulder and Hand) questionnaire will be used in its Spanish version (DASHe) and questions about patient satisfaction with the use of splints.

In the first recruitment visit, following the criteria and specifications of the "Recruitment Plan in relation to patient participation" (Annex III), Optimus 3D will scan the patient with rhizarthrosis to obtain the necessary information with which the model will be created.

The patient, seated, will keep the arm extended on a table, leaving the area of the wrist and hand in the air without support. The wrist will be kept in a functional position, simulating holding a glass. When the clinician verifies the correct position of the affected limb, the scan will begin.

The Optimus 3D technician will rotate the 3D scanner of the ASORCAD equipment around the patient's arm for approximately 1 minute. The scanner connected to a laptop will collect the anatomical data generating a point cloud that will be exported as a mesh (.stl format). This model will be used to begin the custom splint design process.

14. LIMITATIONS OF THE STUDY

The limitations of the study include the following:

- The Eaton-Litter classification is subject to intra-observer and inter-observer variability. This fact can affect the classification of patients. However, it is the most used in the literature.
- The standard splint does not consist of a single model, but there are several available to patients. This fact means that the control group can contain different models. However, this is what happens in routine clinical practice.
- Being a proof of concept study, the comparisons are exploratory.

15. DURATION AND FOLLOW-UP OF THE STUDY

Prior to the beginning of the study, a representative of the promoter or coordinating center will contact the principal investigator and the services involved in the study at each center to review the Protocol together with the data collection notebook (DCN). The objective is to clarify any doubts that may arise prior to the start of the study.

During the course of the study, follow-up visits will be made periodically by a coordinator to check the progress of the study, control the documentation generated, help gather the required data and answer any questions that may arise.

The objective of this procedure is to verify that all documentation and files are up-to-date and guarantee compliance with all protocol requirements and applicable local and national regulations, as well as the competent authorities.

The phases in this study will be:

Tasks	Months					
	1-2	3	4-6	6-7	7-8	8
1.- Documentation: Protocol and DCN						
2.- AEMPS and CREC						
3.- Recruitment and follow-up of patients						
4.- Debugging of the database						
5.- Data analysis						
6.- Results presentation						

Annex III:

Recruitment plan related to patient participation

1. All members of the Orthopedic Surgery and Rehabilitation services will be informed, in the morning session, that initially ALL patients with a first diagnosis of rhizarthrosis in the outpatient clinic must be referred to the Hospital's Outpatient Traumatology Consultations, with symptomatic treatment and with recommendation of relative rest and analgesics. The clinics included are: [name], Rekalde, Deusto, Txurdinaga, Santutxu, Javier Sáenz de Buruaga, Begoña and Bombero Etxaniz.
2. To facilitate the appointment, patients will be referred with PREFERENCE and directed to ORTHOPEDIC SURGERY - RHIZARTHROSIS CLINIC. When doing it in this way, the specific day of the consultation is not given by the administrator of each outpatient clinic, but the request documents are sent by fax to the Hospital's Outpatient Clinics, where the administrators are aware of the study and the days available for citation. In the outpatient clinic, then, the patient receives the information that the appointment will be notified by mail or telephone, and it will take place within a maximum period of 15 days.
3. The administrative staff of the Hospital's Outpatient Clinics will have, each month, at least two consultation spaces for the study of rhizarthrosis, so that no patient waits more than 15 days. These days will be determined with one month in advance, depending on the availability of the doctors, the consultation spaces, and the needs of the service. These inquiries will be notified, also within one month, to the company Optimus 3D. It is not expected to have more than 5 patients each day. The Orthopedic Surgeons who will attend these consultations are doctors [name] and [name]. It is estimated to need about 20 minutes per patient.
4. In the office, it will be determined, from among all the patients, which ones meet all the inclusion criteria and none of the study exclusion criteria. The randomization will be carried out by the Hospital Research Unit. The patients in the experimental group will be scanned the same day of consultation by Optimus 3D company, with the objective of delivering the orthosis as soon as possible, estimating the time from scanning to delivery in 5 working days. Patients who are unable or unwilling to enter the study will be treated according to normal practice.
5. Follow-up consultations will be carried out at one month and at three months, after this first consultation, to evaluate the result of the treatment.

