9. VARIABLES TO RECORD

- The **main variable** is the pain that will be measured, as is usual practice by a visual analog scale from 0 (no pain) to 10 (excruciating pain).

Pain has been chosen as the main variable, under the hypothesis that as the splint is more comfortable it may be worn longer and this would imply a decrease in pain (Annex IV)

- As a **secondary variable**, we will use the DASH questionnaire (10) to assess functional capacity. It is a self-administered questionnaire, which consists of a central body of 30 items that measure function and symptoms. Besides, there are 2 optional modules, with 4 items each, designed to measure the impact of an upper limb injury when playing musical instruments and when doing sports or working. Each item is scored from 1 to 5, with increasing values depending on the intensity of the symptoms. The score of the items in the central body is added to obtain a total score, which can range from 30 to 150 points and which is transformed into a scale from 0 (best possible score) to 100 (worst possible score). Optional modules, where applicable, are scored separately using the same method. The DASH makes it possible to assess the disability perceived by the patient to perform various activities, including activities of daily living and symptoms such as pain, stiffness or loss of strength.

The choice of this variable is justified since it is the questionnaire usually used both clinically and in studies to assess functional capacity (Annex IV).

- To assess patient satisfaction, a satisfaction scale composed of 6 items will be used, each one scored from 0 to 10, that is, a scale of 11 points (11) (Annex IV)

The choice of this variable is justified by the personalized design, with which it is expected that the patients will be more satisfied in the items to be evaluated.

- The evaluation of the time of use, in hours / day, of the different splints will be done by direct question to the patient.

This variable is considered as a surrogate variable, since using the splint for a longer time may possibly improve pain and functionality.

- Finally, the grip and pinch strength will be evaluated before the splint and later, by means of a dynamometer in the consultation.

Other variables that will be included will be:

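### Do two different starting points for the one-month visit, the splint and the first consultation, weaken the comparison of the splints?

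*Protocol*

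**What the plan says.** Two places in the Protocol time the follow-up visits from a named event.

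- Section 10, on the one-month visit: "On the second visit, one month after the splint". On the final visit it gives a window, "at the third month of follow-up (between 11-14 weeks", without saying what the weeks are counted from.
- Annex III, item 5, on both visits: "Follow-up consultations will be carried out at one month and at three months, after this first consultation".

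The abstract and sections 6 and 13 list a recruitment visit, a one-month visit and a three-month visit, and name no start.

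On when the patient gets the device, Annex III item 4 has 3D-arm patients scanned on the day of the consultation, "estimating the time from scanning to delivery in 5 working days". Section 3.2, in a list of product advantages, says that "the 3D model is made in 3 hours and can be in use by the patient in 72 hours". For the other arm, section 10 says only "In the control branch, the doctors prescribe the usual splint for each patient" and gives no supply time.

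**The concern.** One visit appears to have two clocks. In the 3D arm the device arrives after the consultation, so days since the consultation and days in the splint are not the same number. Pain, DASH, satisfaction, time of use and grip strength are all taken at the one-month visit, and section 11 compares groups at follow-up without naming which visit counts.

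The rationale for the main variable depends on wear: section 9 argues that "as the splint is more comfortable it may be worn longer and this would imply a decrease in pain". Yet the wear measure is a daily rate ("The evaluation of the time of use, in hours / day, of the different splints"), which does not show for how many days the patient had the splint. If staff followed different passages, or if the two arms waited differently for their splints, one-month values could rest on unequal exposure and the listed variables would not reveal it.

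**Working it through.** **Inputs**

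- Scan on the day of the first consultation (day 0), delivery after 5 working days: Annex III, item 4.
- Final-visit window of 11 to 14 weeks: section 10.
- Assumptions: a Monday-to-Friday week without public holidays; one month = 30 days; three months = 91 days.

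**Delivery time in calendar days**

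Five working days from any weekday always cross one weekend: 5 + 2 = 7 calendar days. The 72 hours in section 3.2 would be 72 / 24 = 3 days, but that sentence is a general product statement and does not say when the clock starts. I do not use it as a bound.

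**Gap between the two starts, 3D arm**

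| Meaning of the splint in section 10 | Start of the clock | Gap to Annex III |
|---|---|---|
| Prescribed at baseline | day 0 | 0 days |
| Received by the patient | day 7 | 7 days |

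The gap is therefore 0 to 7 days, depending on the reading.

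**One-month visit, receipt reading**

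- Counted from the consultation: possible wear = 30 − 7 = 23 days, and 23 / 30 = 77%.
- Counted from receipt: possible wear = 30 days, and the visit falls on day 30 + 7 = 37 after the consultation.
- Shift: 7 / 30 = 23%.

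**Three-month visit, receipt reading**

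- Window: 11 × 7 = 77 to 14 × 7 = 98 days, a width of 21 days.
- A visit 91 days after the consultation is 91 − 7 = 84 days after receipt. Both 91 and 84 lie between 77 and 98.
- A visit 91 days after receipt is 91 + 7 = 98 days after the consultation, still inside, at the upper limit.
- Shift: 7 / 91 = 7.7%.

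Only visits near an edge would change status. Day 77 after the consultation, for example, is 77 − 7 = 70 days after receipt.

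**Difference between arms**

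Let the control splint arrive L days after the consultation. If both arms are timed from the consultation, the difference in possible wear is 7 − L days. It is 7 if L = 0, zero if L = 7, and reverses if L is larger. The Protocol does not give L, so neither size nor sign can be derived.

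**Reach into the outcomes**

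The DASH in Annex IV asks about the past week. Even at 23 days after receipt, that whole week falls after delivery. The percentages above describe possible cumulative wear, not an effect on any score.

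**The case for a change.** The best case for a change is that visit timing belongs to the protocol and an analysis plan cannot repair it afterwards. Section 10 already calls the first consultation the baseline visit, yet it times the next visit from the splint. Section 9 uses the same expression when it says strength is measured before and after the splint, which suggests the device itself rather than its prescription. The one-month visit has no window to absorb a week, the Protocol does not say that the one-month values are subordinate, and no date of receipt is among the listed variables. One sentence and one date field would settle the matter cheaply.

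Part of this stands. The two texts do differ, and the receipt reading is reasonable. It is not the only one: the sentences just before it in section 10 describe assigning treatment and prescribing the splint at baseline, and section 10 mentions no fitting or delivery visit. On that reading the passages agree.

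The rest does not lead to a better design. Timing from receipt equalises possible wear but leaves time since randomisation unequal by any difference in delivery. Timing from the consultation does the reverse, and counts the wait for the device as part of each strategy. Neither is wrong. A receipt date would be useful descriptive information, but the planned comparisons do not depend on it.

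**Conclusion.** The wording is loose, and no change to the plan follows. The discrepancy is at most about 7 days in the 3D arm, on the assumptions that the splint in section 10 means its receipt and that delivery takes the estimated 5 working days; a longer delivery would widen it. It is zero if prescription is meant. It weighs noticeably only on the one-month visit. At the final visit it is 7.7% of the follow-up, and a visit at 13 weeks is in window on either clock. No bias between arms can be shown, because the control supply time is not given.

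The study tests no specific hypotheses (section 8), is not designed to evaluate efficacy (section 6), and calls its comparisons exploratory (section 14). Its conclusions would be equally sound under either timing, provided both arms are handled alike. A team would ordinarily settle on one start for everyone when booking visits. If the text is revised for other reasons, the two sentences can be aligned then.
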